Methods : This is a prospective compare study. 54 EMT-Ps, are involved to evaluate the impact of airway management on CPR quality. The Study uses SALAD training tool for training. The SALAD training tool include Nasco Intubation CPR manikin, which could vomit by pumping liquid into distal esophagus, and HQCPR feedback machine. Two scenarios were simulated. CPR and ETI in an airway with regurgitation (oropharyngeal regurgitation scenario) and CPR and ETI in an airway without regurgitation (clean airway scenario). All EMT-Ps were assigned to participate initially in one of the scenarios. After all EMT-Ps had finished the first scenario, they switched to the other. Three EMT-Ps formed a resuscitation team and played one of the following roles: airway manager, first compressor, or second compressor. In each scenario, each EMT-P was required to take a turn playing all three roles. During each simulation, the airway manager performed BVM ventilation, and the first and second compressors alternately provided chest compression for every five cycles of CPR, with a compression-to-ventilation ratio of 30:2. After the first five cycles of CPR, the airway manager was asked to perform intubation during

the ongoing chest compression to minimise intubation-associated interruption of chest compression. If necessary, the airway manager could request a pause of the ongoing chest compression. If intubation was not successful, the airway manager performed BVM ventilation twice and then reattempt intubation. After intubation, the airway manager used the BVM to check the lung distention to confirm successful intubation. Each simulation was ended after successful or failed intubation. Failed intubation was defined as either oesophageal intubation or three unsuccessful attempts.

The primary outcomes were CPR quality metrics, namely chest compression fraction (CCF), chest compression depth, chest compression rate, and longest interruption time. The secondary outcomes were the intubation success rate and intubation time.

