Each CPR-intubation sequence comprised two segments: a compression segment and a hands-off segment. Presents the rules for determining the start and end of a CPR-intubation sequence. CCF was defined as the proportion of time spent on chest compression in each CPR-intubation sequence. The longest interruption time was defined as the longest hands-off duration in each sequence. An intubation attempt was defined as the insertion of the laryngoscope blade into the mouth and its subsequent withdrawal from the mouth. Intubation time was defined as the period between the start and the end of an intubation attempt. The time spent checking the endotracheal tube position by manual ventilation through the endotracheal tube was not included in the CPR-intubation sequence.

Two video cameras were setup to record the entire simulation process. Two observers reviewed the video records independently to identify the start and end of each CPR-intubation sequence, any intubation attempts, and the hands-off and compression segments of each sequence. Disagreements were resolved by reaching mutual consensus. The HQCPR application on an Android device recorded chest compression depth, rate, and interruptions (defined as no chest compression [hands off] for >1 s). The data from both the video recording and the HQCPR application were used in subsequent analysis. Continuous data are presented as medians with interquartile ranges, and categorical data are presented as frequency counts and percentages. The continuous data were compared using the Wilcoxon rank sum test in the first CPR-intubation sequence and the Mann-Whitney U test in the second and third sequences. The McNemar test was used to compare the intubation success rate in the first sequence, and Pearson's chi-square test was used for the second and third sequences. The continuous data from all three CPR-intubation sequences were compared using the Kruskal-Wallis test. Post hoc analysis was performed using Conover's test.

The association of CPR quality metrics with successful intubation was evaluated using a Cox proportional hazards regression model. The results of multivariate analyses are presented as hazard ratios (HRs) with corresponding 95% confidence intervals (CIs). A two-tailed $P < 0.05$ indicates statistical significance. MedCalc Statistical Software version 19.2. (MedCalc Software, Ostend, Belgium) was used for data analysis.

Effect :

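### For compression depth and rate, the named rank sum test ignores both the pairing of the scenarios and the possible sharing of compressors within teams, so its error rate is not controlled at 5%

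*Protocol*

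**What the plan says.** All the relevant text is in the Methods of the Protocol.

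- Size and teams: "54 EMT-Ps, are involved to evaluate the impact of airway management on CPR quality"; "Three EMT-Ps formed a resuscitation team and played one of the following roles: airway manager, first compressor, or second compressor".
- Rotation: "In each scenario, each EMT-P was required to take a turn playing all three roles".
- Crossover: "After all EMT-Ps had finished the first scenario, they switched to the other".
- Who compresses: "the first and second compressors alternately provided chest compression for every five cycles of CPR".
- Primary outcomes: "chest compression fraction (CCF), chest compression depth, chest compression rate, and longest interruption time".
- Analysis of first-sequence continuous outcomes: "The continuous data were compared using the Wilcoxon rank sum test in the first CPR-intubation sequence". Significance is two-sided at 0.05.

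The number of runs, the unit of analysis and any allowance for team or compressor are not stated. The sentence that introduces the rules for the start and end of a sequence has lost its subject, probably a figure, so those rules cannot be read here.

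**The concern.** Depth and rate are produced by the people compressing. Three people fill the six compressor places of a team's three runs in a scenario, and the same people return for the other scenario. Two kinds of dependence follow.

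- **Between scenarios.** Someone who compresses deeply in one scenario tends to do so in the other. A rank sum test ignores this and will usually be too conservative.
- **Within a team.** If both compressors contribute to the first sequence, any two of a team's runs share one person. Suppose people differ in how their compressions change from one scenario to the other. Each person's change then enters two of the run differences, and a test that counts 54 independent differences gives P values that are too small.

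The two faults act in opposite directions, so the direction of the net error is unknown. Correcting only the pairing removes the conservative part and leaves the inflating part. At stake is whether a chance shift in a few compressors is declared an effect of the soiled airway, or a real effect is missed, on half of the primary outcomes.

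**Working it through.** **Structure, from the Protocol.** 54 / 3 = 18 teams. Three roles taken in turn give 3 runs per team per scenario, and 18 × 3 = 54 runs per scenario (derived, not stated). Each run has 2 compressor places: 54 × 2 = 108 places, and 108 / 54 = 2 per EMT-P, one as first and one as second compressor.

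**Assumptions.** Teams and rotation are the same in both scenarios, there is no true scenario effect, and variation is normal. The first compressor supplies a share w of the first-sequence value and the second supplies 1 − w. The Protocol gives neither w nor any variance, so ranges are shown.

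**Baseline.** The plan's only error-rate figure is 0.05. With no compressor effects, simulation reproduces it for both tests (first row of the table).

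**Signed-rank on 54 run pairs, by formula.** Let δ be a person's change between scenarios. A run difference is wδ₁ + (1 − w)δ₂ plus run noise. Without noise, the ratio of the true to the assumed variance of the mean difference is DE = 1 / [w² + (1 − w)²], and the error rate is 2 × [1 − Φ(1.96 / √DE)].

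- w = 0.5: DE = 1 / (0.25 + 0.25) = 2.0, error 16.6%.
- w = 0.7: DE = 1 / (0.49 + 0.09) = 1.72, error 13.6%.
- w = 0.8: DE = 1 / (0.64 + 0.04) = 1.47, error 10.6%.
- w = 0.9: DE = 1 / (0.81 + 0.01) = 1.22, error 7.6%.
- w = 1.0: DE = 1, error 5.0%.

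With noise and equal shares, let s be the part of the run-difference variance that comes from compressor-by-scenario effects. Two runs of a team then correlate at s/2, and DE = 1 + s. For s = 0, 0.25, 0.5, 0.75 and 1 the error is 5.0%, 8.0%, 11.0%, 13.8% and 16.6%. A team-by-scenario effect, outside this model, moves DE toward 3 and the error toward 25.8%.

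**Rank sum, direction.** At equal shares, let V be the stable compressor variance, U the scenario-specific one and E the run noise. The true-to-assumed variance ratio is (U + E) / [(V + U)/2 + E]. For V:U:E = 8:0:1 it is 1/5 = 0.2 (far too conservative). For 2:2:0 it is 2/2 = 1 (the two faults cancel). For 0:2:0 it is 2/1 = 2 (inflated).

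**Simulation** (18 teams, 10,000 replicates per row, rejection rates in %):

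| V : U : E, shares | Rank sum, 54 v 54 | Signed-rank, 54 pairs | Signed-rank, 18 team means |
|---|---|---|---|
| 0 : 0 : 1, 50/50 | 5.02 | 5.05 | 4.98 |
| 2 : 0 : 1, 50/50 | 0.78 | 4.97 | 4.99 |
| 8 : 0 : 1, 50/50 | 0.03 | 4.85 | 4.54 |
| 0 : 0.5 : 0.75, 50/50 | 7.79 | 7.57 | 4.58 |
| 0 : 1 : 0.5, 50/50 | 11.02 | 10.86 | 4.78 |
| 0 : 2 : 0, 50/50 | 16.50 | 16.55 | 4.98 |
| 2 : 2 : 0, 50/50 | 5.64 | 16.13 | 5.44 |
| 4 : 1 : 0, 50/50 | 0.37 | 16.97 | 5.15 |
| 1 : 1 : 0, 80/20 | 2.40 | 10.30 | 4.46 |
| 1 : 1 : 0, one compressor only | 0.76 | 5.03 | 4.84 |

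The Monte Carlo standard error near 5% is √(0.05 × 0.95 / 10,000), about 0.2 percentage points.

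**The case against.** The strongest reply has four parts.

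1. **Sharing within the first sequence is not established.** Compressors change every five cycles, and "After the first five cycles of CPR, the airway manager was asked to perform intubation during" places the start of intubation at that same changeover. If the sequence begins there and ends before the next changeover, one person supplies all of it. Each EMT-P then contributes once per scenario, and the paired test holds 5%. This stands, because the rules that would settle it are not in the text at hand.
2. **Rotation alone does not inflate the paired test.** Stable differences between compressors cancel in the pairs. Inflation needs people to differ in their change between scenarios, and the Protocol gives no figure for that. This stands too: s is in effect an unknown within-team correlation.
3. **Pairing was probably intended.** Success in the first sequence is compared with McNemar's test. The Mann-Whitney test, which is the rank sum test under another name, is reserved for later sequences. So a signed-rank test may have been meant. That would answer the pairing fault but not the sharing.
4. **A SAP may set the unit of analysis.** It may, but the Protocol itself names a test that does not fit its design, so this does not remove the point.

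A reader might infer that the planned test has a 16% false-positive rate. The documents do not support that. The rank sum test reaches about 16–17% only with no stable compressor differences, equal shares and no run noise. Where stable differences dominate it is far below 5%.

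**Conclusion.** The point holds as a mismatch between test and design, not as a known inflation. The first-sequence depth and rate values are dependent between scenarios. They are also dependent within teams if both compressors contribute to that sequence. The named test allows for neither.

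- Rank sum as written: from 0.03% to about 16–17%, depending on which variation dominates.
- Signed-rank on 54 run pairs: 5% if compressor differences are stable or one compressor supplies the sequence, up to about 16–17% under a compressor-only model with equal shares.
- Signed-rank on 18 team differences: 4.5–5.4% throughout.

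Nor should 16.6% be read as an absolute ceiling, since a team-by-scenario effect could exceed it. All these figures rest on assumed variances and on teams and rotation staying the same across scenarios, which is the natural reading of the Methods but is not spelled out. The change should be made because it is sound whichever way the unknowns fall. Confidence in the size of the problem is only moderate.

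**What to change.** For compression depth and rate, state in the analysis paragraph that the team is the unit. Average each team's three first-sequence runs within each scenario, and compare the 18 within-team soiled-minus-clean differences with the Wilcoxon signed-rank test. State also that team membership is the same in both scenarios, and restore the rules for the start and end of a sequence.

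A mixed model on the run values is an alternative, not an equivalent. It would need scenario as a fixed effect, random effects for team and team-by-scenario, and multiple-membership effects for compressor and compressor-by-scenario, because each run value may come from two people. It may also need software other than the package named.

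The cost is one or two sentences and a minor extra analysis step, with no new participants or data, provided that team and role were recorded for each run. P values will rest on 18 teams. If there is in fact no sharing within the first sequence, a little power is lost: in a simulation with one compressor per sequence and an effect of 0.4 SD, power was 77% on 18 team means against 81% on 54 pairs.

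### The protocol names an unpaired test for first-sequence continuous outcomes in a crossover, probably a slip for Wilcoxon signed-rank

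*Protocol*

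**What the plan says.** Only the protocol is available. Its Methods section describes a crossover of 54 EMT-Ps between a regurgitation scenario and a clean-airway scenario: "After all EMT-Ps had finished the first scenario, they switched to the other". On roles it says: "Three EMT-Ps formed a resuscitation team and played one of the following roles: airway manager, first compressor, or second compressor", and "In each scenario, each EMT-P was required to take a turn playing all three roles". On outcomes: "The primary outcomes were CPR quality metrics, namely chest compression fraction (CCF), chest compression depth, chest compression rate, and longest interruption time". Intubation time is a secondary outcome.

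The statistical paragraph later in Methods says the continuous data are "compared using the Wilcoxon rank sum test in the first CPR-intubation sequence and the Mann-Whitney U test in the second and third sequences". It then turns to the binary outcome: "The McNemar test was used to compare the intubation success rate in the first sequence", with Pearson's chi-square for the later sequences.

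**The concern.** The continuous-data sentence assigns one test to the first sequence and a differently named test to the second and third, as though they differed. They do not. The Wilcoxon rank sum test is the Mann-Whitney U test, and both assume two independent samples.

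The first-sequence samples are not independent, because each EMT-P contributes one first sequence as airway manager in each scenario. As written, no paired test is named for any of the four primary outcomes or for intubation time. Someone who follows the text literally would analyse crossover data as if two separate groups had been studied. A reader cannot tell which test stands behind the primary P values.

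**Working it through.** The protocol gives no effect size, SD, correlation or power, so there is no stated figure to reproduce. The check has three parts.

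**1. Are the two named tests different?** With n = 54 per scenario, the rank sum W and the statistic U satisfy U = W − n(n+1)/2, where n(n+1)/2 = 54 × 55 / 2 = 1,485. On one simulated data set, W − 1,485 = 1,190 and U = 1,190. The normal-approximation P value without continuity correction is 0.0996 under both names. They are one test.

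**2. What does the rest of the text imply?**

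| Outcome type | First sequence | Second and third sequences |
|---|---|---|
| Intubation success | McNemar (paired) | Pearson chi-square (unpaired) |
| Continuous | Wilcoxon rank sum (unpaired) | Mann-Whitney U (same test, unpaired) |

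A paired-then-unpaired pattern fits the design. Every EMT-P has a first sequence in both scenarios, which gives 54 complete pairs. A simulation ends at success or failure, so only some EMT-Ps reach the later sequences. The binary row follows this pattern and the continuous row does not. Reading the first entry as signed-rank would restore it.

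**3. What if the test is run as named?** The inputs from the protocol are 54 EMT-Ps, teams of three (54 / 3 = 18) and a two-sided 0.05 level. The assumed inputs are normal data with SD 1, a shift of 0.4 SD, a within-EMT-P correlation rho, an intraclass correlation (ICC) of the within-EMT-P differences inside a team, and teams that stay fixed. Each setting used 20,000 simulated data sets, with both tests by normal approximation with continuity correction.

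Independent pairs (ICC 0):

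| rho | Rank-sum type I error | Rank-sum power | Signed-rank power |
|---|---|---|---|
| 0 | 5.2% | 51% | 51% |
| 0.3 | 2.1% | 52% | 66% |
| 0.5 | 0.8% | 53% | 81% |

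In 4,000-set runs, the signed-rank type I error lay between about 4.5% and 5.6% at every rho from 0 to 0.7. With a 0.5 SD shift in the same runs, power was 73% against 83% at rho 0.3, and 78% against 94% at rho 0.5 (rank-sum first).

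Clustered pairs (18 teams of three, ICC 0.2):

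| rho | Type I error, rank-sum / signed-rank | Power, rank-sum / signed-rank | Signed-rank power held to a true 5% |
|---|---|---|---|
| 0.3 | 4.8% / 9.4% | 52% / 64% | 52% |
| 0.5 | 2.2% / 9.6% | 53% / 77% | 67% |

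At rho 0.3 the whole apparent gain of 64 − 52 = 12 points comes from inflated type I error. At rho 0.5, 77 − 67 = 10 of the 77 − 53 = 24 points do.

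A large-sample formula agrees. The true variance relative to the variance each test assumes is about (1 − rho)(1 + 2·ICC) for rank-sum and 1 + 2·ICC for signed-rank. The type I error is 2(1 − Φ(1.96/√factor)). At rho 0.3 and ICC 0.2 the factors are 0.7 × 1.4 = 0.98 and 1.40, which give 4.8% and 9.8%.

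**The case against.** The strongest reply is that this is a one-word terminology error. Naming two different tests makes sense only if one was meant to be paired, and McNemar in the next sentence points the same way. On that reading the right test is run and no result changes. The harm needs the less likely reading plus a positive correlation that the protocol does not give. Even then, with independent pairs, the literal test is conservative: it costs power but creates no false positives. With clustering in teams, signed-rank can exceed its nominal level while the literal test stays below 5% in the two settings simulated. Clustering and the pairing unit are also matters that a separate analysis plan may cover.

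Much of this stands. A slip is the likelier explanation, the simulated figures illustrate and do not estimate, and signed-rank does not deal with clustering.

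Two things do not follow. First, this is not a detail left for later: the protocol names a specific test, for every primary outcome, that does not fit the design it describes. Second, the literal test's apparent protection against clustering is an accident of two errors cancelling. By the formula above, at ICC 0.2 and rho 0 its factor is 1 × 1.4 = 1.40, so its type I error is about 9.8%, the same as for signed-rank.

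**Conclusion.** The text is wrong as written and should be corrected. That rests on the identity of the two tests and on the crossover described in Methods, and it needs no assumption. That signed-rank was intended is a well-supported inference, not something the protocol states.

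The consequence ranges from none (signed-rank intended and run) to a loss of power on the four primary outcomes and intubation time (named test run, positive within-EMT-P correlation, independent pairs). For an assumed 0.4 SD shift, that loss is about 66 − 52 = 14 points at rho 0.3 and 81 − 53 = 28 points at rho 0.5, and nothing at rho 0. If results also cluster within teams, neither the direction nor the size of the effect can be settled from the protocol.

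**What to change.** In the statistical paragraph, replace the first-sequence test for continuous data with the Wilcoxon signed-rank test on the within-EMT-P difference (regurgitation minus clean), paired by airway manager. If that was always the intention, say that the name is being corrected.

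Add one sentence stating whether teams and role order were the same in both scenarios, and what unit is paired for compression depth and rate. Pairing by airway manager is cleanest for CCF, longest interruption and intubation time. Depth and rate come from the teammates, since "the first and second compressors alternately provided chest compression for every five cycles of CPR".

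The cost is one phrase and one sentence, with no new data. The correction leaves clustering within teams unaddressed, and under clustering the signed-rank test can still exceed 5%.

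### The Kruskal-Wallis comparison across sequences 1-3 treats failure-selected, overlapping groups as independent, and the one unselected comparison (sequence 1, which is paired) is given an unpaired test

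*Protocol*

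**What the plan says.** The Methods section has every EMT-P act as airway manager in both scenarios. After an unsuccessful attempt the airway manager ventilates and tries again. The simulation stops at success, at oesophageal placement, or after the third unsuccessful attempt.

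The primary metrics are defined sequence by sequence: "CCF was defined as the proportion of time spent on chest compression in each CPR-intubation sequence", and "The longest interruption time was defined as the longest hands-off duration in each sequence".

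The statistical paragraph then fixes the tests:

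- Scenarios compared in sequence 1: for continuous data the "Wilcoxon rank sum test in the first CPR-intubation sequence"; for success, "The McNemar test was used to compare the intubation success rate in the first sequence".
- Scenarios compared in sequences 2 and 3: for continuous data "the Mann-Whitney U test in the second and third sequences"; for success, "Pearson's chi-square test was used for the second and third sequences".
- Across sequences: "The continuous data from all three CPR-intubation sequences were compared using the Kruskal-Wallis test", then "Post hoc analysis was performed using Conover's test".

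One two-tailed 0.05 threshold covers all of these. Nothing in the paragraph marks the later sequences as conditional on earlier failure.

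**The concern.** Under the stopping rule, a second or third sequence exists only for an EMT-P who has already been unsuccessful in that scenario, without oesophageal placement. The sequences are therefore nested subsets of the same people, and each is filtered by the outcome of the one before. Kruskal-Wallis and Conover's test assume separate, independent groups.

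The filter matters if airway-manager skill drives both success and the metric. That is plausible for chest compression fraction (CCF) and longest interruption, because the airway manager may ask for compressions to pause. It is weaker for depth and rate, which the compressors deliver. The Protocol itself plans a Cox model relating CPR metrics to successful intubation, so independence of the two cannot be assumed. What is at stake is a reported deterioration of CPR quality over attempts that only reflects who is left.

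The Background also expects soiling to lower first-pass success, so the scenario itself helps decide who reaches sequence 2. Sequence 1 escapes all of this, but the test named for its continuous data ignores the pairing.

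**Working it through.** The Protocol gives no success rates, standard deviations or effect size, so there is no planned figure to reproduce. Apart from the 54 EMT-Ps, the teams of three and the stopping rule, every input below is an assumption.

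**1. Who is in each sequence.** 54 / 3 = 18 teams. Each EMT-P manages the airway once per scenario, giving 54 first sequences per scenario. Ignoring oesophageal endings, expected entrants to sequence 2 are 54 × (1 − p), where p is first-pass success.

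| Assumed p, clean / soiled | Clean entrants | Soiled entrants |
|---|---|---|
| 0.80 / 0.65 | 54 × 0.20 = 10.8 | 54 × 0.35 = 18.9 |
| 0.85 / 0.60 | 54 × 0.15 = 8.1 | 54 × 0.40 = 21.6 |
| 0.90 / 0.50 | 54 × 0.10 = 5.4 | 54 × 0.50 = 27.0 |

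In simulation, clean entrants to sequence 3 average 0.6-4.3 and number fewer than 5 in 57-100% of trials. The two expected counts in that row of the chi-square table add up to the row total, so both are then below 5.

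**2. Across-sequence test with no true effect.** Metric = skill + team + residual, with total variance 1, team share 0.20 and skill share 0, 0.10 or 0.30. Success: logit P = a + b × skill (in SD), with b = 0.5, 1.0 or 1.5. There is no scenario or sequence effect and there are no oesophageal endings; 1500 replicates per setting. The table gives the Kruskal-Wallis rejection rate at 0.05 in the soiled scenario, with the range taken over the three pairs of success rates.

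| b | Skill share 10% | Skill share 30% |
|---|---|---|
| 0.5 | 5-6% | 7-8% |
| 1.0 | 7-9% | 17-21% |
| 1.5 | 10-13% | 29-36% |

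At skill share 0 the rate is 3-4%. The Protocol does not say whether the test is run per scenario. Pooled over both scenarios, at shares of 10-30%, it rejects in 6-14% (b = 0.5), 10-42% (b = 1.0) and 18-69% (b = 1.5), and in 3-5% at share 0.

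**3. Scenario tests in sequence 2.** Under the same inputs the soiled-minus-clean bias is 0.03-0.29 SD, in the direction of the soiled airway looking better. Fewer people fail in the clean airway, so those who do are the more strongly selected. Mann-Whitney rejects in only 3-8%. The success contrast is 13-16, 23-26 and 37-42 points against the assumed 15, 25 and 40, so it is hardly distorted.

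**4. Sequence 1: paired data, unpaired test.** Let r be the within-EMT-P correlation of the metric between scenarios: r = 0.20 + 0.10 = 0.30, or 0.20 + 0.30 = 0.50. A test that ignores r has a null statistic with SD √(1 − r), so its true size is approximately P(|Z| > 1.96/√(1 − r)).

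- r = 0.30: 1.96/0.837 = 2.34, size about 1.9%.
- r = 0.50: 1.96/0.707 = 2.77, size about 0.6%.

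The simulation gives 0.5-3% for rank sum and 4-7% for signed-rank.

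For power at an assumed 0.4 SD difference, the paired noncentrality is 0.4 × √54 / √(2(1 − r)):

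- r = 0.30: 2.94/1.183 = 2.48, Φ(2.48 − 1.96) = 70%.
- r = 0.50: 2.94/1.00 = 2.94, Φ(2.94 − 1.96) = 84%.

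Simulated signed-rank power is a little lower, 65% and 80%. Rank sum gives about 52% in both cases.

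**5. Stronger inputs.** A separate simulation used success of 0.9/0.6, 0.8/0.5 and 0.6/0.3, 5% oesophageal placement per attempt, b = 1-2 and within-person correlation 0.5-0.8. Kruskal-Wallis rejected in 12-95% within one scenario. With b = 0 and correlation 0.5 it rejected in 1.0-3.8%, so the inflation comes from selection and not from the repeated use of the same people.

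**The case against.** The objective is soiled against clean. The test that is materially inflated compares sequences, and if run per scenario it does not compare scenarios at all. This stands, and it limits the point.

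The size is wholly assumed: at b = 0.5 the per-scenario rate is only 5-8%. This stands too. The 12-95% above comes from stronger links and supports the direction, not a particular size.

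That sequence k is attempt k is an inference from the three-attempt limit, because the start and end rules for a sequence are not shown. It is a reasonable inference but has to be declared.

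Rank sum and Mann-Whitney U are the same test. Contrasting them in one sentence, beside McNemar for the same sequence, suggests that signed-rank was meant. A reader might infer that the wrong test will certainly be run. The text does not settle that, and the power loss applies only if it is followed as written.

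An SAP may cover small counts or a whole-simulation comparison, so their absence is not a fault here. That does not rescue the named tests, because the Protocol fixes those itself.

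**Conclusion.** The point holds for the across-sequence comparison and for the sequence-1 test name. Given the sequence-equals-attempt reading and a link from skill to both success and metric, Kruskal-Wallis can be significant with no sequence effect in about 5-36% of trials per scenario and 6-69% pooled. Without the link it is not inflated. Confidence is good on the structure and low on the size.

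A reader might infer that selection also produces false evidence that soiling harms CPR quality. The documents and the check do not support that: the sequence-2 scenario bias is modest, rejection stays at 3-8%, and the direction would mask harm. Nor does the point invalidate the trial's main question, since sequence 1 includes every EMT-P and is free of this selection. The rank sum test there is conservative and costs power; it does not create false positives.

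**What to change.** In the statistical paragraph:

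- Name the Wilcoxon signed-rank test, paired by EMT-P, for the continuous data in sequence 1, and make it the main scenario comparison of CPR metrics.
- Report the across-sequence comparison and the scenario comparisons in sequences 2 and 3 descriptively, with counts, as conditional on earlier unsuccessful attempts.
- State that sequence k is attempt k, if that is so.

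A fixed-EMT-P model should not replace Kruskal-Wallis as a confirmatory test. It rejects in 7-19% under no effect when an attempt's own execution affects both its metric and its success.

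Optional and supportive only: a paired whole-simulation CCF comparison shown beside the number of attempts, stating whether ventilation pauses between attempts count. Whole-simulation longest interruption is less useful because it partly restates the attempt count (5-36% rejection with no per-sequence effect).

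The cost is wording and reanalysis. The video and HQCPR records already hold the data. The downside is that later-sequence P values are no longer confirmatory.
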